ANNEX 3. ADDITIONAL INFORMATION

A. Lists of Codes to Identify Patients with IBS and IBS Type

Table 4. Read Codes for the Identification of IBS and Constipation

Read Code	Description	Comments
J521000	IBS with diarrhoea	To be used as exclusion criteria
14CF.00	History of irritable bowel syndrome (IBS)	To identify potential prevalent cases
Eu45324	Psychogenic IBS	Unfrequently used, check for constipation
J521.00	Irritable colon–IBS	Preferred code, check for constipation
J521.13	Spastic colon	Unfrequently used, check for constipation
J521.11	IBS	Preferred code, check for constipation
19C..11	Constipation symptom	Preferred code, combined with IBS
19C..00	Constipation	Preferred code, combined with IBS
19C2.00	Constipated	Unfrequently used, combined with IBS
19CZ.00	Constipation NOS	Unfrequently used, combined with IBS
J520z00	Constipation NOS	Third choice, combined with IBS
J520.00	Constipation – functional	Second choice, combined with IBS
J520100	Chronic constipation with overflow	Unfrequently used, combined with IBS
J520000	Acute constipation	Unfrequently used, combined with IBS
J520200	Chronic constipation without overflow	Unfrequently used, combined with IBS
J520300	Drug induced constipation	Unfrequently used, combined with IBS
E264500	Psychogenic constipation	Unfrequently used, combined with IBS
J520y00	Other specified constipation	Unfrequently used, combined with IBS
1962.00	Colicky abdominal pain	Second choice as code in IBS
1971.00	Central abdominal pain	Third choice as code in IBS
1972.00	Epigastric pain	Third choice as code in IBS
196..00	Type of GIT pain	Unfrequently used
196..11	Abdominal pain type	Unfrequently used
1968.00	Abdominal discomfort	Third choice as code in IBS
1969.00	Abdominal pain	Second choice as code in IBS
197..13	Site of abdominal pain	Unfrequently used
197A.00	Generalised abdominal pain	Second choice as code in IBS
197C.00	Lower abdominal pain	Third choice as code in IBS
197Z.00	Site of GIT pain NOS	Unfrequently used
1963.00	Non-colicky abdominal pain	Unfrequently used
196Z.00	Type of GIT pain NOS	Unfrequently used
196..12	Type of GIT pain - symptom	Unfrequently used
1976.00	Right flank pain	Unfrequently used
1975.00	Left flank pain	Unfrequently used

197..11	Flank pain	Unfrequently used
197..12	Iliac fossa pain	Unfrequently used
1977.00	Right iliac fossa pain	Unfrequently used
1978.00	Left iliac fossa pain	Unfrequently used
197B.00	Upper abdominal pain	Unfrequently used
197D.00	Right upper quadrant pain	Unfrequently used

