4763.00	Faeces: mucous present	Unfrequently used
19EH.00	Mucus in faeces	Unfrequently used
198..00	Nausea	Second choice as code in IBS
1982.00	Nausea present	Unfrequently used
198..12	Nausea symptoms	Third choice as code in IBS
198..11	C/O - nausea	Unfrequently used
198Z.00	Nausea NOS	Unfrequently used
R070000	[D] Nausea	Unfrequently used
R070.00	[D] Nausea and vomiting	Unfrequently used
R093000	[D] Abdominal swelling	Unfrequently used
J16y411	Flatulent dyspepsia	Unfrequently used
19D..12	Anal symptoms	Unfrequently used
19D..11	Tenesmus symptom	Unfrequently used
19D..00	Tenesmus	Unfrequently used
19D2.00	Tenesmus present	Unfrequently used
19DZ.00	Tenesmus NOS	Unfrequently used
19E..11	Faeces symptom	Unfrequently used
19E..12	Motions – symptom	Unfrequently used
19E..00	Faeces/motions – symptoms	Unfrequently used
19F..	Diarrhoea symptoms	
19G..00	Diarrhoea and vomiting	
J525.00	Functional diarrhoea	
J43z.	Chronic diarrhoea	
J4z..	Non-infectious diarrhoea	

Abbreviations: IBS=irritable bowel syndrome; IBS-C=IBS predominately with constipation; NOS=unspecified

Patients with IBS will be identified through the following criteria:

- One or more IBS- related codes among the following: J521.00, J521.11, J521.13, Eu45324, 14CF.00.
- Alternatively, a combination of a code of abdominal pain or discomfort (in gray background and regular font) and at least two codes among those reported as “second choice as code in IBS”, “third choice as code in IBS” or “unfrequently used” (in *italics* and gray background).

Patients with only 14CF.00 will identify as prevalent IBS-C patients since the diagnosis date is uncertain.

Patients with IBS-C will be identified through the following criteria:

- Patient with IBS as specified above and one preferred code including the term “constipation”

Patients with IBS and a code for diarrhoea will be IBS-D. Patients with IBS only or meeting both criteria will be IBS-M.

Table 5. ICD-10 Codes for the Identification of IBS and Constipation

ICD-10 Code	Description	Comments
K58	Irritable bowel syndrome (IBS), irritable colon	Preferred code, check for constipation
K58.0	IBS with diarrhoea	To be used as exclusion criteria
K58.9	IBS without diarrhoea; IBS NOS	Preferred code, check for constipation
K59.9	Functional intestinal disorder, unspecified	Not specific
K59.0*	Constipation	To be used in combination with K58, K58.9, and K59.9 to identify IBS predominantly with constipation (IBS-C)

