Abbreviations: IBS=irritable bowel syndrome; IBS-C=IBS predominately with constipation ; NOS=unspecified

Patients with IBS will be identified through the following criteria:

- At least one code K58, K58.9 or K59.9 without code K58.0

Patients with IBS-C will be identified through the following criteria:

- Patient with IBS as specified above and code K.59.0

Patients with IBS-D will be identified through the following criteria:

- Patient with code K58.0

Patients with IBS-M will be all others with IBS but no criteria of IBS-C or IBS-D

Table 6. ICD-9 Codes for the Identification of IBS and Constipation

ICD-9 Code	Description	Comments
564.1	Irritable bowel syndrome (IBS); irritable colon; spastic colon	Preferred code, check for constipation
564.0, 564.00, 564.01, 564.09	Constipation	To be used in combination with 564.1 to identify IBS predominantly with constipation (IBS-C)
787.91	Diarrhoea	To be used in combination with 564.1 to identify IBS predominantly with constipation (IBS-D)

Abbreviations: IBS=irritable bowel syndrome; IBS-C=IBS predominately with constipation; IBS-D=IBS predominantly with diarrhoea

Patients with IBS-M will be identified through the following criteria:

- Code 564.1 without codes for constipation or codes for diarrhoea.

B. Database Feasibility Assessment

This section includes a summary of the databases assessed for use in the linaclotide studies, planned to be implemented in the UK, Spain, and Sweden. The feasibility assessment in Italy as a candidate country is also reported, although the coverage of the data sources investigated was not large enough to accrue sufficient sample size for this study. All databases identified were explored for feasibility and data content, as well as interest and availability in conducting the studies. This section contains the information provided by the candidate data sources contacted for this purpose.

Database Identification

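### The UK Read rules leave J521000 (IBS with diarrhoea) outside IBS and never assign it to IBS-D, although the matching ICD-10 code K58.0 makes a patient IBS-D by itself

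*Protocol*

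**What the plan says.** Section 9.3.4 of the protocol refers to Tables 4 to 6 in Annex 3 for identifying IBS, and Annex 3.A adds written rules for each coding system.

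**UK (Read codes, Table 4).** The table entry is "J521000 IBS with diarrhoea To be used as exclusion criteria". The code-based route to IBS is "One or more IBS- related codes among the following: J521.00, J521.11, J521.13, Eu45324, 14CF.00"; J521000 is not in that list. The other route is an abdominal pain or discomfort code plus at least two further listed symptom codes, and J521000 is not part of it. Typing then works only within IBS. IBS-C needs IBS and one preferred constipation code. For diarrhoea, "Patients with IBS and a code for diarrhoea will be IBS-D". For the rest, "Patients with IBS only or meeting both criteria will be IBS-M".

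**ICD-10 (Table 5).** K58.0, the matching code, carries the same exclusion comment, and the general IBS rule also requires that it be absent. A separate line then defines IBS-D as "Patient with code K58.0". The Read rules have no such line for J521000.

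Sections 9.3.1 and 9.3.2 list the diagnosis of IBS and its type as a subgroup and baseline variable. Section 9.7.1 names two constipation subgroups: chronic constipation without IBS-C, and constipation codes only, the latter read as possible laxative use. Section 9.7.2 uses IBS-C versus other conditions as the contrast in the Cox models.

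**The concern.** J521000 names both the disease and its subtype, yet in the UK it leads to neither. The comment in Table 4 does not say whether the code excludes a patient from IBS-C, from IBS altogether, or from something else. It cannot be a cohort exclusion, because the criteria in Section 9.2.2.1 exclude no diagnosis.

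At stake is the UK description of IBS and its type, which belongs to a primary question. Section 4.9 plans aggregated analyses across the three countries for the primary objectives. Sweden codes diagnoses in ICD-10, as do Spanish general practitioners (Section 4.7), so the same recorded diagnosis would be IBS-D there and could be unclassified in the UK. Two programmers could both follow Annex 3.A and report different UK counts. For some users the choice also decides whether they count as IBS-C, which is the indication variable in the time-to-event models.

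**Working it through.** There is no sample size, power or event figure to reproduce. The check applies the Annex 3.A rules to every code pattern that contains J521000.

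**Inputs.** Three features vary, each yes or no: another qualifying IBS route (one of the five codes, or the symptom combination); a preferred constipation code; a separate diarrhoea code. That gives 2 × 2 × 2 = 8 patterns.

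**Readings of the Table 4 comment.** A: J521000 has no effect on type. B: J521000 counts as a diarrhoea code. C: J521000 bars the patient from IBS.

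**Comparator.** The ICD-10 rule for a patient with K58.0, which gives IBS-D whatever else is recorded.

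| Other IBS route | Constipation code | Diarrhoea code | A | B | C | K58.0 rule |
|---|---|---|---|---|---|---|
| no | no | no | not IBS | not IBS | not IBS | IBS-D |
| no | no | yes | not IBS | not IBS | not IBS | IBS-D |
| no | yes | no | not IBS, constipation | not IBS, constipation | not IBS, constipation | IBS-D |
| no | yes | yes | not IBS, constipation | not IBS, constipation | not IBS, constipation | IBS-D |
| yes | no | no | IBS-M | IBS-D | not IBS | IBS-D |
| yes | no | yes | IBS-D | IBS-D | not IBS | IBS-D |
| yes | yes | no | IBS-C | IBS-M | not IBS, constipation | IBS-D |
| yes | yes | yes | IBS-M | IBS-M | not IBS, constipation | IBS-D |

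**Results.**

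1. With no other IBS route (rows 1 to 4), all three readings agree: the user is not IBS and so cannot be IBS-D. A separate diarrhoea code does not help, because the UK IBS-D rule starts from IBS.
2. With another IBS route (rows 5 to 8), no row has the same answer under all three readings. Row 7 gives three different answers, one of them IBS-C.
3. Agreement with the K58.0 rule is 1 of 8 patterns under A (row 6), 2 of 8 under B (rows 5 and 6) and 0 of 8 under C.

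These are counts of patterns, not of patients. The protocol gives no frequency for J521000.

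**The case against.** The strongest reply is that the ICD-10 rules also take the explicit diarrhoea code out of the general IBS group, so the UK exclusion is no anomaly. That stands: the difference is a single line, the one that then labels K58.0 as IBS-D. Without that line in the Read rules, the exclusion leaves the UK patient with no type at all.

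Several stronger readings are tempting and are not supported.

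- **All UK users with J521000 are lost from IBS-D.** Only those with no other qualifying route certainly are. Users who also have, say, J521.00 or the symptom combination can still be typed, unless the code is read as a bar to IBS.
- **Users with J521000 and a constipation code are reported as constipation-only.** Section 9.7.1 gives no operational rule for that subgroup, and a record holding J521000 arguably does not contain constipation codes only. They may enter it; the text does not settle the matter. As for chronic constipation without IBS-C, users with no other IBS route are non-IBS-C whether they are called IBS-D or non-IBS, so the omission does not change that membership.
- **UK IBS-D counts cannot be compared with the other countries because of this code.** Comparability has other limits: the Read, ICD-10 and ICD-9 rules build IBS-D differently, and Sweden has no primary care data. Section 9.9 already expects some misclassification of type. Correcting J521000 removes one avoidable difference, not all of them.
- **A patient count can be put on it.** Any share of users with J521000 would be arbitrary. The natural base, 2,674 projected UK users by the end of 2016, was not being reached according to Section 9.5.

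It is also fair that IBS-D is not one of the off-label groups listed in Section 8.2 or the subgroups in Section 9.7.1, and that the IBS-C count does not change for users with no other IBS route. This limits the consequence but does not make the rule correct.

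**Conclusion.** The point holds in a limited form. As written, a UK user with J521000 and no other qualifying IBS route is counted as neither IBS nor IBS-D, under every reading tested. A user with J521000, another IBS code and a preferred constipation code is IBS-C, IBS-M or non-IBS depending on what the exclusion means and whether a separate diarrhoea code is present. The equivalent K58.0 patient is IBS-D in all these cases.

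The effect is misclassification of a baseline variable in one country and, for some users, of the indication variable in the Cox models. Its size in patients cannot be computed from the protocol. The conclusion rests on taking the Annex 3.A rules literally and on J521000 and K58.0 denoting the same diagnosis, as their descriptions in Tables 4 and 5 indicate. Because the protocol itself fixes these rules, this is not a detail left to the analysis plan. It should be corrected before the UK classification is programmed.

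**What to change.** Four changes of wording are needed:

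1. Add to the Read rules: *Patients with J521000 will be classified as IBS-D*, regardless of other codes, parallel to the K58.0 rule.
2. Change the Table 4 comment on J521000 to: *excludes from IBS-C and IBS-M; identifies IBS-D*.
3. State how IBS-D patients identified by J521000 or K58.0 enter the overall IBS total, and apply this identically in all countries. At present both codes lie outside the group that the rules call IBS.
4. In Section 9.7.1, state that a J521000 record disqualifies a patient from the constipation-codes-only subgroup.

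The first change has one consequence to accept openly. A UK user with J521000 and a preferred constipation code becomes IBS-D, whereas treating J521000 as an IBS code and a diarrhoea code would make that user IBS-M under the UK rule for meeting both criteria. IBS-D is what matches K58.0. Making it conditional on having no constipation code would not match, and would leave the combination without a clear type.

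The cost is a few lines in Annex 3.A and Section 9.7.1 and a small program change. No new data are needed.

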7. RATIONALE AND BACKGROUND

IBS is a chronic, relapsing gastrointestinal condition characterised by abdominal pain, bloating, and changes in bowel habits. The first presentation of patients with IBS symptoms to a physician is usually in the 30 to 50-year age group, and there is a decrease in reporting frequency among older subjects (Drossman et al., 2002; IBS Global, 2009). Typically, women are diagnosed with IBS two or three times as often as men in most studies and all population-based studies have reported a female predominance (Keeling & Fielding, 1975; Thompson, 1984; 1997; Saito et al., 2002). Moreover, women make up 80% of the population with severe IBS (Longstreth & Wolde-Tsadik, 1993). Prevalence estimations vary with the diagnostic criteria used, and in the UK were estimated between 9.5% and 22% (Spiller et al., 2007).

IBS can be classified according to Rome III criteria, on the basis of the stool's characteristics: IBS-D; IBS-C; and IBS-M. Patients can transition among these subgroups (IBS Global, 2009). Approximately one third of IBS corresponds to IBS-D, one third to IBS-C and one third to IBS-M (Tillisch et al., 2005). When there is insufficient abnormality of stool consistency to meet the criteria for any of the above, IBS is said to be unsubtyped (Longstreth et al., 2006).

Prior IBS treatments were limited to lifestyle modifications, psychological interventions, and symptomatic treatments (e.g., laxatives, anti-diarrhoeals, and anti-spasmodic agents), or drugs unauthorised for this indication in some of the countries. In a recent review, current IBS-C treatment options showed limited efficacy, and the risk-benefit profile of early 5-Hydroxytryptamine 4 (5-HT₄) agonists restricts clinical use (Fortea et al., 2013).

The commercialisation of linaclotide (Constella[®]), a guanylate cyclase-C receptor agonist with visceral analgesic and secretory activities, was approved as the first medicine authorised for the symptomatic treatment of moderate-to-severe IBS-C in adults in the European Union (EU).

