 - Bacterial/viral/parasite lab information, when available (positive versus negative or no information)

For prevalence of chronic comorbidities, prior diagnoses, or history of digestive surgery at index date, the patient's entire medical history will be explored.

9.3.3. *Linaclotide Treatment Outcomes*

Secondary outcomes of this study will be linaclotide treatment patterns. The linaclotide exposure information is characterised by the linaclotide days of supply. Days of supply will be ascertained from the prescription/dispensation information recorded in the databases and the recommended dose (one capsule of linaclotide 290 µg taken once per day) and calculated by dividing the quantity prescribed/dispensed by the daily dose. Days of supply of one prescription/dispensation are expected to be around 28 days since the 28-capsule pack will be the most widely used package size. If package size is unknown, then the median duration for patients with this information will be used (and if no median can be estimated then 28 days will be used).

Linaclotide prescription patterns of interest are:

- Discontinuation of linaclotide: defined as no prescription of linaclotide in the period of 1.5 times the number of days of supply of the last linaclotide prescription following its expiry date (Sikka et al., 2005; Peterson et al., 2007): for example, for a 28-day prescription, no new prescription in the 43 days after the expiry date of the prescription supply. The date of discontinuation is the day after the date of expiry of the last linaclotide prescription. Time to discontinuation (permanently during the study period or temporarily) is the interval between the date of the first linaclotide prescription and the date of discontinuation. Discontinuation

will be reported separately for those who permanently discontinue during the study period and for those who discontinue temporarily and subsequently restart on linaclotide (see below).

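### The IBS subtype rules in Annex 3.A contradict each other and Section 9.3.4, so the IBS-C group behind the off-label question and the indication contrast is not uniquely defined

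*Protocol*

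**What the plan says.** Section 9.3.4 states that no Read, ICD-9 or ICD-10 code is specific to IBS-C, and that potential cases will be found by combining an IBS code with a constipation code. It sets no further condition on the constipation code.

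Annex 3.A turns this into rules.

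- **Read codes (UK), IBS-C:** "Patient with IBS as specified above and one preferred code including the term" constipation. In Table 4 two constipation codes carry the note "Preferred code, combined with IBS". Functional constipation (J520.00) is marked "Second choice, combined with IBS", and the rest are marked as third choice or infrequent, again for combination with IBS.
- **Read codes, history code alone:** "Patients with only 14CF.00 will identify as prevalent IBS-C patients since the diagnosis date is uncertain".
- **Read codes, residual:** "Patients with IBS only or meeting both criteria will be IBS-M".
- **ICD-10, residual:** every IBS patient meeting neither the IBS-C nor the IBS-D rule is IBS-M.
- **ICD-9, IBS-M:** "Code 564.1 without codes for constipation or codes for diarrhoea".

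Section 7 describes a further group: "When there is insufficient abnormality of stool consistency to meet the criteria for any of the above, IBS is said to be unsubtyped". None of the three algorithms contains it.

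Section 8.1 makes the extent of off-label use with respect to the indication a primary question. Section 8.2 names the off-label groups and sets the indication contrast as IBS-C diagnosis versus other. Section 9.7.1 describes a subgroup with chronic constipation but not IBS-C, among subgroups chosen partly for potential off-label use.

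**The concern.** A classifier that feeds a primary question should give one answer per patient. Here two programmers working from the same text could build different IBS-C groups, and the three code systems treat the same clinical record differently. Section 4.9 then aggregates the three countries for the primary objectives.

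Some patients who meet the Section 9.3.4 description of IBS-C would be denied that label, and others would receive it with no constipation code. Either error moves patients across the IBS-C versus other line in the Cox models, and some of the first kind can enter a subgroup described for potential off-label use. Labelling IBS with no subtype code as IBS-M also treats an absence of coding as evidence of mixed bowel habit.

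**Working it through.** The protocol states no off-label percentage or classification accuracy to reproduce, so the check sets the rules side by side.

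**Step 1: count the qualifying Read codes.** Table 4 lists 12 constipation codes: 2 preferred (19C..11, 19C..00), 1 second choice (J520.00), 1 third choice (J520z00) and 8 infrequent. 2 + 1 + 1 + 8 = 12. Read literally, the annex rule excludes 12 − 2 = 10 codes that Section 9.3.4 and the table's own comments would admit. ICD-10 and ICD-9 have no such restriction.

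**Step 2: classify four coding patterns.**

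| Codes recorded with IBS | Read | ICD-10 | ICD-9 |
|---|---|---|---|
| Constipation only | IBS-C if 19C..11 or 19C..00; otherwise not IBS-C | IBS-C (K59.0) | IBS-C (any of four listed codes) |
| Diarrhoea only | IBS-D | IBS-D (K58.0) | IBS-D (787.91) |
| Both | IBS-M if the constipation code is preferred; otherwise IBS-D | IBS-D, because K58.0 removes the patient from the IBS definition used for IBS-C | Meets IBS-C and IBS-D, and is excluded from IBS-M |
| Neither | IBS-M, but also IBS-C if the only code is 14CF.00 | IBS-M | IBS-M |

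The last two rows show the problem. The same pattern of codes gets three different treatments when both symptoms are coded. Under ICD-10 and ICD-9 the IBS-M group consists solely of patients with neither code, so it contains no one with recorded mixed habit.

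**Step 3: follow a UK patient with IBS and J520200 (chronic constipation without overflow).** Under Section 9.3.4 this patient is IBS-C. Under the annex rule the patient is not, because J520200 is not preferred. The patient then goes to other in the Cox contrast and can be counted in the Section 9.7.1 subgroup of chronic constipation without IBS-C. A patient with IBS and J520.00 is likewise denied IBS-C and goes to other.

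**Step 4: follow a UK patient with only 14CF.00.** This code is in the list that establishes IBS on its own. With no other code the patient falls under the residual rule (IBS-M), yet the preceding sentence says IBS-C. The reason given, an uncertain diagnosis date, bears on whether the case is prevalent and says nothing about subtype.

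**Step 5: is the net direction fixed?** Let p be the true IBS-C share among users, and Se and Sp the sensitivity and specificity of the IBS-C label. The apparent non-IBS-C share is 1 − [p·Se + (1 − p)(1 − Sp)]. It exceeds the true share only if p(1 − Se) > (1 − p)(1 − Sp). None of these inputs is in the protocol. As assumed values to show the sign only, p = 0.7 and Se = 0.9 (true share 30%) give:

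- Sp = 1.0: 1 − 0.63 = 37%
- Sp = 0.9: 1 − (0.63 + 0.03) = 34%
- Sp = 0.7: 1 − (0.63 + 0.09) = 28%

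The sign changes within this range, so the rules alone do not determine it.

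**The case against.** The best defence is that this is a descriptive study with an openly imperfect classifier. Section 9.3.4 speaks of potential cases, the footnote in Section 9.3.2 reports the IBS-C proportion when possible, and Section 9.9 expects misclassification between IBS types and between IBS-C and chronic constipation. The two-code limit touches only the UK, about 28% of projected patients (2,674 / 9,665). Eight of the ten excluded codes are marked infrequent, including both whose descriptions name chronic constipation. These points stand and limit the size. They do not answer the contradictions: Section 9.9 concerns what the data can show, while the conflicts lie in rules that the protocol itself fixes.

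A reader might infer that the off-label estimate is inflated overall. The documents do not support that. Patients with IBS and no subtype code belong to none of the off-label groups named in Section 8.2. They count as off-label only if Section 8.1 is read as anything other than IBS-C, which the protocol neither says nor excludes. Several rules also push the other way: 14CF.00 alone gives IBS-C, IBS can be inferred from symptom codes, and the non-specific K59.9 plus K59.0 counts as IBS-C.

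A reader might also infer that one old diarrhoea code will move IBS-C patients to IBS-M, because under Section 9.3.2 the "entire medical history will be explored". That sentence covers chronic comorbidities, prior diagnoses and digestive surgery, and does not clearly extend to transient symptom codes. A short look-back for diarrhoea alone would favour IBS-C.

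Finally, an unsubtyped label in Section 7 rests on stool consistency, so a group defined by absent codes should not borrow that name. Renaming it also leaves it outside IBS-C in the Cox contrast. Both points are fair and shape the fix.

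**Conclusion.** The subtype rules are inconsistent as written and should be reconciled before the IBS-C group is built. Three faults are established from the text: preferred versus any constipation code in the UK, two labels for patients with only 14CF.00, and no category for IBS without a recorded subtype, with three treatments of patients who have both symptom codes.

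These faults can bias the off-label description and the IBS-C versus other contrast. One component has a known direction: UK patients with IBS and a non-preferred chronic constipation code can be wrongly counted as potentially off-label. Its size cannot be stated, because the protocol gives no code frequencies. The net direction across all rules and countries is unknown. Attenuation of the indication hazard ratio would follow in general only if misclassification were unrelated to outcome, which the documents do not show. The SAP is not at hand, and the absence of sensitivity analyses from the protocol is no part of this conclusion.

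**What to change.** 1. Align the Read rule in Annex 3.A with Section 9.3.4 and Table 4, so that the listed constipation codes annotated for combination with IBS qualify for IBS-C. Keep the preferred-only definition as a sensitivity analysis.
2. Remove the IBS-C label for patients with only 14CF.00 and no constipation code. They can still be flagged as prevalent IBS.
3. Add a category such as IBS, subtype not recorded, to all three algorithms, and state where it falls in the IBS-C versus other contrast.
4. Adopt one common rule for patients with both constipation and diarrhoea codes.
5. Report off-label use by indication with the subtype-not-recorded group counted once as on-label and once as off-label.

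The cost is code-list wording, one extra table row and a second run of the off-label table, with no new data. The off-label figure becomes a range, and the broader list may admit some acute (J520000) or drug-induced (J520300) constipation, which the preferred-only sensitivity analysis would help to show.
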